# **PROTOCOL REVISION HISTORY**

Version	Date	Description of Change	Brief Rationale
1.0	29-Mar-22	Not Applicable	Initial Version
2.0	19-Apr-22	Exclusion Criteria Modification	Addition of Exclusion Criteria to Exclude Employees, Family Members or Personal Associate of the Sponsor
3.0	16-May-22	Exclusion Criteria Modification	Concomitant Medication Clarification and Hospitalization Language Clarification
4.0	19-May-22	Revision to Baseline Instrument Inclusion Criteria	Participants are not excluded due to PHQ-9 & QIDS-SR baseline scores outside of moderate range
5.0	08-Jun-22	Modification to the study target population	Allow enrollment of patients with severe depression and corresponding higher baseline BDIII scores

# 1.2.1 List of Investigative Sites and Roles of Parties

The FW-200-05 trial is a decentralized clinical investigation due to the COVID-19 pandemic. As Principal Investigator, [name] will oversee the study conduct and the safety of the subjects. Climb will establish and maintain the electronic patient reported outcomes (ePRO)/electronic data capture platform, provide clinicians to qualify subjects for study participation, and provide investigative staff for non-clinical subject assistance including subject training on device handling. Climb will also support Fisher Wallace Laboratories, Inc. (Sponsor) with coordinating the shipping of investigational devices to subjects. NAMSA (CRO) will be responsible for supporting the Sponsor with study management activities.

#### **1.3** OVERVIEW OF CLINICAL INVESTIGATION

Full Title	Cranial Electrotherapy Stimulation for the Treatment of Major Depressive Disorder in Adults
Short Title	CES-MDD
Protocol Number	FW-200-05
Protocol Version	Version 5.0
Study Sponsor	Fisher Wallace Laboratories, LLC. [name]
Study Purpose	This prospective, fully remote, randomized, controlled, triple-blind (subject, Principal Investigator, Sponsor) pivotal study is designed to evaluate the safety and efficacy of the Fisher Wallace Stimulator FW200 to deliver Cranial Electrotherapy Stimulation (CES) for the treatment of moderate to severe Major Depressive Disorder (MDD) in adults.
Investigational Product	Fisher Wallace Stimulator® FW-200
Study Objective	To demonstrate the safety and effectiveness of FW-200 CES selfadministered for the treatment of moderate to severe MDD in adults

Study Endpoints	
 
Primary: 
 
Change in the Beck Depression Inventory Second Edition (BDIII) at week two compared to baseline.
 
Change in the BDI-II at weeks one and four compared to baseline.
 
Change in the Patient Health Questionnaire-9 (PHQ-9) and Quick Inventory of Depressive Symptomatology Self-Report (QIDS-SR) at weeks one, two, and four compared to baseline.
 
BDI-II responder rate at four weeks.
 

	
 
Safety:
 
Determine the rate of device related adverse events.
 

Study Design	Remote, decentralized, randomized, controlled, triple blind (subject, Principal Investigator, Sponsor), pivotal investigation
Inclusion Criteria	
 
Age 21-65 years and a resident of the United States of America
 
Meets DSM-5 diagnostic criteria for moderate to severe Major
 

Exclusion Criteria	
 
History of suicide attempt or active suicidal ideation with plan or intent in the past 30 days.
 
In the opinion of the investigator, considered high risk of suicide
 
Previous hospitalization or institutionalization for mental health condition within one year of study entry.
 
Underwent electronic brain stimulation or neuromodulation within the past one year, including CES, transcranial magnetic stimulation, electroconvulsive therapy, and deep brain stimulation
 
Modification of prescription medications that affect the nervous system including those for mental health issues within 30 days of study entry. A patient who has been on a stable dose of prescription medications that affect the nervous system or being used for a mental health issue for at least 30 days prior to study entry and are not expected to modify their medication while on the trial are allowed to participate.
 
Use of recreational drugs, hypnotics, steroids, and/or marijuana products in the past 30 days
 
History of alcohol use disorder or other substance use disorder in the past 12 months
 
Females currently pregnant or planning to conceive during study participation, or unwilling to comply with birth control requirements
 
Known history of trigeminal neuralgia
 
Implanted with an electronic device such as a defibrillator, deep brain stimulator, or pacemaker
 
Unstable medical condition including any condition requiring hospitalization or change in treatment in the prior 30 days
 

	
 
13. Legally blind and/or deaf and without in-home care service to assist with study participation
 
14. Meets M.I.N.I. assessment criteria for, or has been diagnosed with, any of the following: Bipolar I disorder, bipolar II disorder, other specified bipolar and related disorder, panic disorder, agoraphobia, social anxiety disorder (social phobia), obsessive-compulsive disorder, posttraumatic stress disorder, alcohol use disorder in the past 12 months, substance use disorder (non-alcohol) in the past 12 months, any psychotic disorder (e.g., schizophrenia, schizoaffective disorder), major depressive disorder with psychotic features, anorexia nervosa, bulimia nervosa, binge-eating disorder, generalized anxiety disorder, any cognitive or developmental disorder (e.g., autism, Down's Syndrome), any personality disorder or psychiatric disorder that may interfere with study participation
 
15. Current participation in another investigational study or participated in an investigational study within the past 30 days
 
16. In the opinion of the investigator, may not be able to comply with study requirements
 
17. Any employee, family member, or personal associate of the Sponsor or their designees conducting the study
 

Target Population/ Sample Size	Adults ages 21-65 years. A total of 250 evaluable subjects (approximately 1:1 allocation) will be included in this study. Subject will be located in the United States and have a diagnosis of moderate to severe Major Depressive Disorder.
Number of Site(s)	One investigative site in the US with subject activities conducted via a decentralized/remote method.
Study Duration	Estimated subject participation time is approximately 6 weeks: 2-week lead-in period followed by 4 weeks of treatment.
Statistical Methods	Continuous data will be summarized with mean, standard deviation, median, minimum, maximum, and number of evaluable observations. Categorical variables will be summarized with frequency counts and percentages. Confidence intervals may be presented, where appropriate, using the t-distribution for continuous data and ClopperPearson Exact method for categorical variables. The primary endpoint is the change in BDI-II at week 2 compared to baseline. Analysis will be based on a linear model for change, adjusted for each subject's baseline value, comparing the randomized groups.

# **2** INTRODUCTION

# 2.1 BACKGROUND

Mental health treatment was the greatest healthcare cost in the U.S. prior to the pandemic, more than cancer, heart disease, or diabetes. Mental health care costs have further increased in the past two years. According to the Centers for Disease Control and Prevention (CDC), the rate of clinical depression among US adults has more than tripled since the COVID-19 pandemic began (Czeisler et al., 2020). The U.S. is in the midst of an unprecedented mental health crisis, and the American public requires treatment options that are effective, safe, and efficiently delivered to patients. There was a large, unmet clinical need for treatment of depression before COVID-19, and there will continue to be such a need after the pandemic is brought under control.

There are significant gaps in the delivery of care to patients suffering from depression. In the U.S., the majority of patients with depression who are treated with antidepressant medication receive their prescription not from a board-certified psychiatrist, but from their primary care physician. These clinicians are usually not responsible for making psychiatric diagnoses, and do not formally monitor side effects or evaluate response (Mann, 2011). Cognitive behavioral therapy and other forms of in-person psychotherapy

Version 5.0 08-Jun-2022

are expensive and require a high level of sustained patient engagement in order to be effective. Inadequate access to mental health resources has long been an issue for many segments of the U.S. population. This reality of the U.S. mental healthcare system means that Cranial Electrotherapy Stimulation (CES), as a low risk, home-based intervention, provides a potentially clinically important benefit for treating patients with depression.

Beginning approximately twenty years ago, new, effective forms of neuromodulation became available, some of which the FDA has reviewed for clinical use, including transcranial magnetic stimulation (TMS), deep brain stimulation (DBS), and vagus nerve stimulation (VNS). In the case of CES, which was already commercially available with long track records of safety, a number of pilot studies and a substantial amount of anecdotal evidence supported safety and effectiveness. The development of new neuromodulatory treatments greatly increased interest in the clinical potential of all forms of neurostimulation to treat depression. Scientific and clinical interest also re-focused on older methods of therapy, such as electroconvulsive therapy (ECT), which, like CES, delivers alternating current, albeit ECT delivers an exponentially higher dose of electrical stimulation designed to cause a seizure and thus requires anesthesia to administer. The Fisher Wallace Stimulator delivers a low dose of pulsed alternating current which is comfortable and safe to self-administer and is intended to be used by the patient twice a day to treat depression.

In recent years, animal and clinical research on CES for alleviating depression has increased, and it has been found that higher frequencies can overcome the impedance of the human skull (Mindes, 2015). Neurophysiological effects have been studied using concurrent brain magnetic resonance imaging (Ghobadi-Azbari, 2020) and electroencephalography (EEG) (Merlet, 2013; Miniussi, 2012). Computational modeling (Datta, 2013 a, b; Khadka, 2020) of stimulation effects using models of electrical behavior in tissues of the head, skull and brain provides additional data suggesting that stimulation may have beneficial impact.

CES is a low-cost, non-invasive, wearable form of low intensity neural stimulation that has been used clinically for over 100 years (Mindes, 2015). This body of evidence from use of CES, and comparison with other neuromodulation methods, indicate that CES is a safe form of neural stimulation that causes minimal side effects. This large body of evidence also suggested possible benefits of regular CES for a range of neuropsychiatric indications, including depression.

The Fisher Wallace Stimulator was cleared by the FDA for the treatment of depression, anxiety and insomnia in 1990 and has been on the market for 32 years - under the brand Liss Cranial Stimulator from 1990-2007, and under the brand Fisher Wallace Stimulator from 2007 to the present. Over 100 published scientific articles analyzing the safety and effectiveness of CES are available on PubMed.gov. Uncontrolled and controlled clinical studies as well as many mechanistic studies have been performed in the US, with better quality research being generated over the past decade. These studies investigated and evaluated the effectiveness and safety of CES devices in various patient populations, as well as possible biological mechanisms of action.

#### **2.2** STUDY RATIONALE

While the precise mechanism of action for CES is not yet known, there is substantial research and decades of use showing that CES does have physiological effects on the brain, and that those effects are consistent with CES alleviating depression. This study will leverage the opportunities and efficiencies of the telehealth environment to investigate the benefits of CES for adults with moderate to severe MDD. In doing so, the study will more accurately represent the real-world experience of patients using CES, as CES devices are typically prescribed for home use, and more psychiatric care is being provided via telemedicine.

This prospective, fully remote, randomized, controlled, triple-blind study is designed to evaluate the safety and efficacy of FW-200 self-administered Cranial Electrotherapy Stimulation (CES) in adults with moderate to severe Major Depressive Disorder (MDD).

#### **3** INVESTIGATIONAL DEVICE

#### **3.1** INTENDED USE

The Fisher Wallace Stimulator FW-200 is a non-invasive medical device intended to treat adult patients with moderate to severe Major Depressive Disorder (MDD). The FW-200 is a prescription device for use at home by the patient without a medical professional, though the device may also be used in a professional health care setting or extended care facility.

#### **3.2** POPULATIONS AND INDICATIONS FOR WHICH THE INVESTIGATIONAL DEVICE IS INTENDED

The indicated use is Cranial Electrotherapy Stimulation in adults (ages 21-65 years) for 20 minutes twice daily, upon waking for the day and at bedtime, to reduce symptoms of moderate to severe MDD.

#### **3.3** DESCRIPTION OF THE INVESTIGATIONAL DEVICE

The FW-200 is a fixed output version of the commercially available FW-100 which has variable output. Whereas the commercially available FW-100 is able to deliver output at four different Levels, 1-4, the FW200 only outputs at Level 2.

The FW-200 device consists of the following components (also refer to figures below):

- CES device controller
- Electrode receptacle with sponge
- Electrode lead wires (red and black)
- Sponges 4-pack
- Velcro headband
- Carry case
- User guide
- AA batteries

Figure 1: FW-200 CES Device

Figure 2: Headset Electrode Wires and Applicator Sponges

Figure 4: FW carry case Figure

Figure 5: Sponges 4-pack

Figure 6 demonstrates the functional principle of the FW-200 device. The controller contains a dial for users to turn the device on and off. An LED panel on the controller displays the output level of the device and confirms the device is on. Figure 8 displays images of patients wearing and handling the FW-200 device components. The controller is connected to two sponges that are secured to the patient's head with a headband.

Figure 6: Functional Block Diagram

Figure 7: Wearing and Handling of the FW-200

As described in the User Guide, the patient's scalp and hair must be clean before electrode application to minimize the risk of irritation caused by placement of the electrodes. The sponge electrodes, as well as the scalp and hair beneath the electrodes, must be wet for electrode conductivity to occur. New headsets are provided with pre-installed sponges in the white plastic sponge receptacles. The sponges provided are dehydrated and will expand when wet.

After snapping the white sponge receptacles to the wires and inserting the other ends of the wires into the top of the device, patients must saturate the sponges with water. The electrode sponges should be replaced every two weeks, or if they become stained or appear degraded in any way.

The patient places the headband on the head so that it sits above the eyebrows. The wet electrodes, in the receptacles with attached wires, are placed beneath the headband, above the sideburns. The bottom of the electrode should be in line with the top of the ear. The physiological location of electrode placement is the squamous temporal bone above the very posterior part of the zygomatic arch.

Once the wet sponge electrodes are placed securely beneath the headband, with wires connected, the device is turned on by rotating the dial. The dial is rotated counterclockwise to go from the OFF to ON position (there is a click when the dial is rotated to ON). The green ON light should illuminate and the first and second (Level #2) yellow indicator lights should also flashes yellow, indicating Level #2 output. If the green ON light does not illuminate, the user should replace the batteries. If the yellow indicator lights do not illuminate, the user should press the electrodes against his/her head to expel more water, or rewet the sponges or tighten the headband.

Depending on skin sensitivity, patients may or may not feel a sensation of stimulation (prickly sensation, warmth) when the device is used on the head at Level #2. Although the dial does show four levels, all settings will administer Level #2 stimulation to the study subject.

Study subjects will use the device twice daily: once for 20 minutes after waking up for the day and once again for 20 minutes before going to bed.

# **3.3.1** ACCESSORIES

The FW-200 is provided as a complete kit. For any device replacement needs (lead wires, sponge receptacles, sponge pack or headband), a new complete kit will be shipped.

#### **3.3.2** CONDITIONS OF USE

Users will be provided instructions regarding the conditions of this use. The environment where the system is used should be one that has the following operating conditions:

- Temperature range: 41 to 95°F (5 to 40°C)
- Relative humidity range: 10% to 93%, non-condensing

Do not allow water to enter the device. The Fisher Wallace Stimulator® should not be exposed to environmental conditions where the system may get wet. Operation in close proximity (e.g., within 1m) to a shortwave or microwave therapy equipment may reduce the output performance of the device.

Keep the device out of reach of children. Electronic monitoring equipment such as ECG monitors and ECG alarms may not operate properly when CES stimulation is in use. High frequency surgical equipment may not be used when CES stimulation is in use. This device is not suitable for use with oxygen or in the presence of a flammable anesthetic mixture with air or oxygen, or with nitrous oxide.

#### **3.3.3** CLEANING THE DEVICE

The device and headset require cleaning for reuse. Reference the User Guide for the cleaning instructions. Investigative staff and subjects will be trained on the cleaning process during device handling training.

#### 3.3.4 SIGNAL FORMS

Both the monopolar waveforms in the FW-200 will make use of three frequencies: 1) 15 kHz; 2) 15 Hz; and 3) 500 Hz. The 15 kHz frequency refers to the carrier frequency. The 500Hz frequency controls the on and off times of the carrier. The 15Hz frequency controls the polarity reversal of the combined 15kHz and 500Hz signals. The voltage amplitude of the output signal is the same for both polarities. The combined voltage amplitude will be twice the monopolar form.

#### **3.3.5 VOLTAGE AND CURRENT OUTPUT**

The FW-200 has been designed to provide a constant current. This is done with a fixed voltage and a resistive feedback circuit called the Constant Current Controller. Users should be receiving approximately 2 mA peak-to-peak (in the monopolar scheme) and 4 mA peak-to-peak (in the bipolar scheme).

Voltage and current are directly related to each other by the resistance of the load (in this case the human head). Therefore, a constant current controller was needed to address the variability in the resistance of the human head. The constant current controller adjusts its own resistance so that the human head plus the controller will produce a fixed current for the Output voltage. At a resistance of 100 Ohms, the voltage output is approximately 400 mV. At 200 Ohms, the voltage output is double, approximately 800 mV.

The average current output relates to the modulation of the signal. If the voltage was applied constantly, the average current would be 2mA because it is being modulated the average current is reduced by each duty cycle: 50% due to the 15kHz on/off carrier modulation; 50% due to the 500Hz on/off modulation of the carrier and 75% due the off time between the 15Hz polarity reversal.

That provides an average current of 0.375 mA.

#### **3.3.6 ELECTRONICS/CONTROLLER**

Figure 9 below is a block diagram of the electronics system. It demonstrates the key connections between the major systems that make up the Printed Circuit Board Assembly (PCBA). The batteries provide power for the entire system operation. The microcontroller (MCU) takes input from the Dip Switch and a Rotary switch. In turn, it controls the light emitting diodes (LEDs) and the complementary metal oxide semiconductor (CMOS) Analog Switch. The MCU will also power the LEDs to visually affirm that the device is on. The Voltage Regulator takes power from the Batteries and increases the voltage for the output circuitry. The Microcontroller produces the three frequencies and modulates the Output using the CMOS Analog Switch. The Analog Switch is able to both turn on and off the voltage as well as swap the Output's polarity. The Constant Current Controller maintains current through the Output by the use of a resistive feedback circuit. This circuit varies its own resistance so that 2mA is maintained even if there are differences at the output. The Microcontroller will drive the Buzzer to indicate the end of the session.

Figure 9: Electronics Block Diagram

#### **3.3.7 SOFTWARE**

The FW-200 contains firmware. All functions of the device are controlled by integrated circuits.

# **3.4** MANUFACTURER OF THE INVESTIGATIONAL DEVICE

The FW-200 is manufactured by Fisher Wallace Laboratories, Inc. via its contract manufacturer.

#### 3.5 MODEL NAME AND NUMBER INCLUDING SOFTWARE VERSION AND ACCESSORIES

The names, model numbers and versions of the components of the FW-200 to be used in this study are provided in Appendix 1.

#### 3.6 DEVICE TRACEABILITY DURING AND AFTER THE CLINICAL INVESTIGATION

The FW-200 and the accessory components are identifiable by lot number, equipment number, or serial number. These component lot numbers and reference numbers will be tracked by the Sponsor using a device accountability log. Return of investigational products will be reconciled against clinical study shipping logs.

The Sponsor or designee shall keep records documenting the receipt, use, and return of the investigational devices. Dispositions of all investigational devices will be maintained in the ePRO.

The FW-200 devices and accessories will remain within the expiry date for the duration of the clinical study. FW-200 devices and accessories will be replaced in study site inventory and returned to the Sponsor prior to their expiry date. Replacement FW-200 devices will be provided as necessary.

#### 3.7 DEVICE MATERIALS IN CONTACT WITH TISSUES OR BODY FLUIDS

The FW-200 materials that will be in direct contact with tissues are listed Appendix 1.

#### 3.8 SUMMARY OF TRAINING AND EXPERIENCE NEEDED TO USE THE INVESTIGATIONAL DEVICE

The FW-200 components are intended for use at home by study subjects.

Prior to the subject receiving the study device, a member of the investigative team will verify that the subject has completed a self-paced video training detailing the device components, how to use them, and how to clean them for personal reuse. Additionally, investigational staff will conduct a live demonstration via video conference of the device including a review of the User Guide with the subject. The subject will be required to confirm his/her understanding of device usage and cleaning process prior to using the FW200 independently. The investigational team will be available to answer device-related questions upon request from a subject. Subject training completion will be documented in the ePRO.

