If the screened subject's data is within the acceptable range for the BDI-II, the subject will advance to scheduling a meeting with a clinician from the investigative team. Via teleconference, the clinician will administer the M.I.N.I. assessment and the Diagnostic and Statistical Manual of Mental Disorders (DSM-5) evaluation.

If the clinician identifies that the subject's results do not meet both M.I.N.I. and DSM-5 criteria for moderate to severe MDD, the subject will be notified that they are no longer eligible for study participation. Additionally, during the live interview, the clinician may deem the subject a screen failure should they no longer meet all inclusion criteria or meet any exclusion criteria.

If the clinician diagnoses the subject with moderate to severe MDD based on the results of the M.I.N.I. and DSM-5 assessments, and determines that the subject meets all other eligibility criteria, the subject will be prescribed study treatment by the clinician and be randomized to a study treatment arm (sham device or active treatment device). Only eligible subjects will be enrolled in the study, randomized to a treatment arm, and receive an investigational device shipped directly to them by an unblinded Sponsor designee.

Prior to starting self-administered therapy with the FW-200 sham or active device, subjects will review an online device training video and undergo a live device and ePRO training with investigative staff. The day after successfully completing live training with investigative staff, subjects will begin self-administered therapy twice per day, one 20-minute session after waking for the day and one 20-minute session before going to bed. Each day of study therapy, subjects will confirm in ePRO that they completed both treatment sessions for the day. Subjects will also be asked if there have been any changes to their medications or health status within the past 24 hours. This will be captured as free text to allow subjects to describe any positive or negative (adverse events) experiences during study therapy.

At the following time points, subjects will retake the BDI-II, PHQ-9, and QIDS-SR assessments:

- Week 1 (Day 7 of therapy)
- Week 2 (Day 14 of therapy)
- Week 4 (Day 28 of therapy)

For the Week 1 and Week 2 evaluations, subjects will have 2 additional days to complete the assessments. For the Week 4 evaluation, subjects will have 5 additional days to complete the assessments. Should a

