## 7.3.4 Screening Lead-In and Baseline

Upon signing the informed consent form, subjects will begin the screening lead-in period of 14-days minimum. No data will be collected from the subject during this time; however, the data collected during pre-screening will be saved in ePRO as study eligibility data.

After 14 days of lead-in time, subjects will be prompted to retake the BDI-II and PHQ-9 assessments in ePRO. Subjects will also take a QIDS-SR assessment in ePRO. A subject must have a BDI-II score between 20 and 63, indicating moderate to severe MDD, at both initial pre-screening and baseline to participate in the study.

If the BDI-II assessment score is not within the moderate to severe MDD range, the subject's health will be considered insufficiently stable for study entry. The subject will be notified that they are no longer eligible for study participation and they will be considered a screen failure.

If the screened subject's data is within the moderate to severe MDD range for the BDI-II assessment, the subject will advance to scheduling a meeting with a clinician from the investigative team.

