#### 7.3.6.1 **Device Shipment**

An unblinded investigative staff member who is not associated with any other function of the study will receive the subject's randomization allocation and contact/shipping address information. The study device type, either sham or active treatment, assigned to the subject through the randomization process will be directly shipped to the location requested by the subject by a third party vendor in collaboration with the unblinded investigative staff member.

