# 7.3.7 Subject Training

The subject will be advised to not use the investigational device until after receiving live training. Prior to the live training, the subject will be asked to complete online device training using pre-recorded videos.

Once the subject receives the investigational device, they must participate in a live training with investigative staff to further learn how to correctly place and use the device, clean the device components that will be reused, and complete data collection in ePRO. The trainer will explain that the device is locked

CES-MDD	Version 5.0
FW-200-05	08-Jun-2022

at Level 2 and that the subject may or may not feel a sensation of stimulation, regardless of whether the device is a placebo or active device.

The subject will confirm in ePRO that their training was completed. The trainer will also record in ePRO that training was completed. The subject will continue to have access to the pre-recorded instructional video and usage manual during the study as needed for additional reference and may contact the investigative staff for device handling support during the study.

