# 8.1 ANALYSIS POPULATION

The primary analysis will be based on intent-to-treat, with subjects analyzed as randomized regardless of treatment actually received.

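### The video-training check that Section 3.8 requires before device receipt is missing from randomisation and shipment; completing it in the lead-in would turn video non-completers into screen failures

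*Combined protocol and SAP*

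**What the plan says.** Section 3.8 makes a verified video a precondition of having the device: "Prior to the subject receiving the study device, a member of the investigative team will verify that the subject has completed" the self-paced training.

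The operational sections do not carry this through:

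- Section 7.3.6 randomises once eligibility is confirmed and the prescription is written. Training is not mentioned.
- Section 7.3.6.1 has an unblinded staff member who "will receive the subject's randomization allocation and contact/shipping address information"; the device then "will be directly shipped to the location requested by the subject by a third party vendor". Nothing else triggers shipment.
- Section 7.3.7 sets the video against a different milestone: "Prior to the live training, the subject will be asked to complete online device training using pre-recorded videos". The live session itself follows delivery: "Once the subject receives the investigational device, they must participate in a live training with investigative staff".
- Section 7.1.1 uses a third milestone: "Prior to starting self-administered therapy with the FW-200 sham or active device, subjects will review an online device training video".
- Section 7.3.1 puts the training column after the randomisation column.
- Section 13.3 does hold back shipment for training, but it concerns staff, not subjects.

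Before randomisation there is a lead-in of at least 14 days. Section 7.3.4 says of it: "No data will be collected from the subject during this time". No task is assigned to the subject in that period.

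Two further rules decide what happens to a randomised subject who never finishes the video. Section 7.3.15.1 replaces subjects withdrawn before they receive a device and does not replace those withdrawn afterwards. Section 8.1 makes the primary analysis intent-to-treat, "with subjects analyzed as randomized regardless of treatment actually received".

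**The concern.** Staff cannot tell from these sections when the video check applies, or what becomes of a randomised subject who fails it. In a fully remote trial, some people may stop responding between the eligibility interview and first use. Every such subject already carries an allocation, so the loss falls inside the randomised comparison. With no post-baseline score, multiple imputation has only baseline information for that subject and recovers little.

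The step need not come that late. The video is pre-recorded and self-paced, it needs no device in hand, and every subject must complete it before treatment anyway. The same non-completion discovered before randomisation would be an ordinary screen failure, with no consequence for the analysis set.

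**Working it through.** **1. The two ways of following the text**

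| | 3.8 enforced after randomisation | 7.3.6.1 followed as written |
|---|---|---|
| 3.8 check | Applied | Bypassed |
| Device | Not received | Received; 7.3.7 advises against use before live training |
| Day 0 (first day of treatment, 7.3.1) | None | None unless live training is completed |
| Scheduled Week 2 BDI-II | None | None unless therapy starts |
| If withdrawn (7.3.15.1) | Replaced | Not replaced |
| Primary analysis (8.1) | Still in the randomised cohort | Still in the randomised cohort |

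In the first column, a randomised subject is replaced while 8.1 keeps that subject in the analysis, and no section says how the two fit together. In the second, the loss comes out of the planned number.

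**2. The plan's own sample size (Section 8.5)**

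Inputs: difference 3.2, SD 9, two-sided alpha 0.05, power 80%, 1:1 allocation.

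- n per arm = 2 × (1.960 + 0.842)² × 9² / 3.2² = 124.2, rounded up to 125, so 250 in total.
- Noncentrality at 125 per arm = 3.2 / (9 × √(2/125)) = 2.81. Power is 80.3% by the normal approximation and 79.96% by the noncentral t.

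The stated figure is reproduced. It includes no inflation for loss.

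**3. What loss at the video step would cost**

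The documents give no share d of randomised subjects lost at this step, so d is an assumption. Assume also that 250 are randomised and the lost subjects are not replaced. Two cases:

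- Outcome missing: n per arm becomes 125 × (1 − d). This treats imputation from baseline alone as adding nothing.
- Outcome somehow collected though untreated: the difference becomes 3.2 × (1 − d) with 125 per arm. The plan schedules no such assessment, so this is a pessimistic bound.

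Noncentral t at SD 9:

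| d | Power, outcome missing | Power, untreated but measured | Randomised for 250 evaluable, 250/(1 − d) |
|---|---|---|---|
| 2% | 79.2% | 78.4% | 255.1, so 256 |
| 5% | 77.9% | 75.8% | 263.2, so 264 |
| 10% | 75.7% | 71.2% | 277.8, so 278 |
| 20% | 70.6% | 61.0% | 312.5, so 313 |

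Section 8.5 also reports an SD of about 6.5 from previous data. With that value, power is 97.2% with no loss. At d = 20% it is 93.4% (outcome missing) or 87.3% (untreated but measured).

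**4. What the prior trial can and cannot supply**

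Section 4.2: 275 enrolled, 83 + 78 = 161 with a 4-week assessment, so 114/275 = 41.5% without one. This is loss from all causes by Week 4. It does not isolate the video step, so it is not used as a value of d.

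**The case against.** The strongest case against is that this is a wording gap with little harm behind it.

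- **Replacement.** The target in Sections 7.2.5 and 8.5 is 250 evaluable subjects, and 7.3.15.1 replaces anyone withdrawn before device receipt. Where that happens, the power loss above does not follow. This stands, which is why the figures are conditional on no replacement. It leaves open how replacement fits with 8.1.
- **The sections can be read together.** Finishing the video between randomisation and delivery satisfies 3.8, 7.1.1 and 7.3.7. The training column in 7.3.1 is marked as needing telephone contact, so it probably describes the live session rather than the video. This also stands. One sentence in 7.3.6.1 would remove the contradiction, but a non-completer would still be found only after randomisation.
- **Engagement is already tested.** After the lead-in, subjects must return, complete three questionnaires and attend a clinician interview, and ability to comply is an eligibility criterion. Nothing in the documents shows how many more people a video would screen out.
- **Power may be ample.** Section 8.5 calls SD 9 conservative and expects a further gain from baseline adjustment. Missing-data detail is deferred to a standalone SAP.

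A reader might go further and infer that untrained subjects will use the device. The text does not support that: 7.3.7 advises against use before live training and makes that training mandatory, and 7.1.1 starts therapy only the day after it is successfully completed. A reader might also infer that the comparison is biased. Loss before first use, with subjects blinded, should be roughly balanced between arms. Nor does the 41.5% from the prior trial measure this loss.

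**Conclusion.** The inconsistency is real: Section 3.8 sets a condition that randomisation and shipment do not apply, and the fate of a randomised non-completer depends on which section is followed. Reordering the step is a worthwhile, cheap improvement rather than the repair of a serious flaw.

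Its size is unknown because the documents give no share lost at the video step. Under the no-replacement assumption and SD 9, losing 2% to 10% there costs roughly 1 to 4 percentage points of power. Near SD 6.5 the cost is small. Losses during shipping, at live training or during therapy are untouched by the change. The case for acting rests on the contradiction and on the clash between replacing randomised subjects and analysing as randomised; both need resolving even if very few subjects are affected.

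**What to change.** 1. Place the self-paced video and its staff verification in the lead-in, recorded in ePRO. Amend 7.3.4, which now says no data are collected then.
2. State in 7.3.6 that a subject is randomised only after verified completion; otherwise the subject is a screen failure.
3. Keep the live training after device receipt.
4. Align 3.8, 7.1.1, 7.3.1, 7.3.6.1 and 7.3.7 to this order.
5. In 7.3.15, state how a subject withdrawn between randomisation and device receipt for any other reason is counted, so that the replacement rule agrees with 8.1.

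The cost is one reordered ePRO step and the wording changes. There are three downsides. The gap between the video and first use gets longer, though 7.3.7 keeps the video available and the live session still follows delivery. Some subjects who then fail the clinician interview will have watched it for nothing. The randomised group will be slightly more engaged than it would otherwise have been.
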